Vomiting	Transient or intermittent vomiting with no or minimal interference with oral intake	Frequent episodes of vomiting with no or mild dehydration	Persistent vomiting resulting in orthostatic hypotension OR Aggressive rehydration indicated	Life-threatening consequences (eg, hypotensive shock)

NEUROLOGICAL				
	Grade 1	Grade 2	Grade 3	Grade 4
Alteration in Personality-Behavior or in Mood (eg, agitation, anxiety, depression, mania, psychosis)	Alteration causing no or minimal interference with usual social & functional activities	Alteration causing greater than minimal interference with usual social & functional activities	Alteration causing inability to perform usual social & functional activities	Behavior potentially harmful to self or others (eg, suicidal/homicidal ideation or attempt, acute psychosis) OR Causing inability to perform basic self-care functions
Altered Mental Status For Dementia, see Cognitive and Behavioral/Attentional Disturbance (including dementia and ADD)	Changes causing no or minimal interference with usual social & functional activities	Mild lethargy or somnolence causing greater than minimal interference with usual social & functional activities	Confusion, memory impairment, lethargy, or somnolence causing inability to perform usual social & functional activities	Delirium OR obtundation, OR coma
Ataxia	Asymptomatic ataxia detectable on exam OR Minimal ataxia causing no or minimal interference with usual social & functional activities	Symptomatic ataxia causing greater than minimal interference with usual social & functional activities	Symptomatic ataxia causing inability to perform usual social & functional activities	Disabling ataxia causing inability to perform basic self-care functions
Cognitive and Behavioral/Attentional Disturbance (including dementia and Attention Deficit Disorder)	Disability causing no or minimal interference with usual social & functional activities OR Specialized resources not indicated	Disability causing greater than minimal interference with usual social & functional activities OR Specialized resources on part-time basis indicated	Disability causing inability to perform usual social & functional activities OR Specialized resources on a full-time basis indicated	Disability causing inability to perform basic self-care functions OR Institutionalization indicated
CNS Ischemia (acute)	NA	NA	Transient ischemic attack	Cerebral vascular accident (CVA, stroke) with neurological deficit
Developmental delay – Pediatric ≤ 16 Years	Mild developmental delay, either motor or cognitive, as determined by comparison with a developmental screening tool appropriate for the setting	Moderate developmental delay, either motor or cognitive, as determined by comparison with a developmental screening tool appropriate for the setting	Severe developmental delay, either motor or cognitive, as determined by comparison with a developmental screening tool appropriate for the setting	Developmental regression, either motor or cognitive, as determined by comparison with a developmental screening tool appropriate for the setting

NEUROLOGICAL				
	Grade 1	Grade 2	Grade 3	Grade 4
Headache	Symptoms causing no or minimal interference with usual social & functional activities	Symptoms causing greater than minimal interference with usual social & functional activities	Symptoms causing inability to perform usual social & functional activities	Symptoms causing inability to perform basic self-care functions OR Hospitalization indicated (other than ER visit) OR Headache with significant impairment of alertness or other neurologic function
Insomnia	NA	Difficulty sleeping causing greater than minimal interference with usual social/functional activities	Difficulty sleeping causing inability to perform usual social & functional activities	Disabling insomnia causing inability to perform basic self-care functions
Neuromuscular Weakness (including myopathy & neuropathy)	Asymptomatic with decreased strength on exam OR Minimal muscle weakness causing no or minimal interference with usual social & functional activities	Muscle weakness causing greater than minimal interference with usual social & functional activities	Muscle weakness causing inability to perform usual social & functional activities	Disabling muscle weakness causing inability to perform basic self-care functions OR Respiratory muscle weakness impairing ventilation
Neurosensory Alteration (including paresthesia and painful neuropathy)	Asymptomatic with sensory alteration on exam or minimal paresthesia causing no or minimal interference with usual social & functional activities	Sensory alteration or paresthesia causing greater than minimal interference with usual social & functional activities	Sensory alteration or paresthesia causing inability to perform usual social & functional activities	Disabling sensory alteration or paresthesia causing inability to perform basic self-care functions
Seizure: (new onset)	NA	1 seizure	2–4 seizures	Seizures of any kind that are prolonged, repetitive (eg, status epilepticus), or difficult to control (eg, refractory epilepsy)

NEUROLOGICAL				
	Grade 1	Grade 2	Grade 3	Grade 4
Seizure: (pre-existing) For Worsening of Existing Epilepsy the Grades Should Be Based on an Increase from Previous Level of Control to Any of These Levels	NA	Increased frequency of pre-existing seizures (non-repetitive) without change in seizure character OR infrequent breakthrough seizures while on stable meds in a previously controlled seizure disorder	Change in seizure character from baseline either in duration or quality (eg, severity or focality)	Seizures of any kind that are prolonged, repetitive (eg, status epilepticus), or difficult to control (eg, refractory epilepsy)
Seizure – Pediatric < 18 Years	Seizure, generalized onset with or without secondary generalization, lasting < 5 minutes with < 24 hours post ictal state	Seizure, generalized onset with or without secondary generalization, lasting 5–20 minutes with < 24 hours post ictal state	Seizure, generalized onset with or without secondary generalization, lasting > 20 minutes	Seizure, generalized onset with or without secondary generalization, requiring intubation and sedation
Syncope (not associated with a procedure)	NA	Present	NA	NA
Vertigo	Vertigo causing no or minimal interference with usual social & functional activities	Vertigo causing greater than minimal interference with usual social & functional activities	Vertigo causing inability to perform usual social & functional activities	Disabling vertigo causing inability to perform basic self-care functions

MUSCULOSKELETAL				
	Grade 1	Grade 2	Grade 3	Grade 4
Arthralgia See also Arthritis	Joint pain causing no or minimal interference with usual social & functional activities	Joint pain causing greater than minimal interference with usual social & functional activities	Joint pain causing inability to perform usual social & functional activities	Disabling joint pain causing inability to perform basic self-care functions
Arthritis See also Arthralgia	Stiffness or joint swelling causing no or minimal interference with usual social & functional activities	Stiffness or joint swelling causing greater than minimal interference with usual social & functional activities	Stiffness or joint swelling causing inability to perform usual social & functional activities	Disabling joint stiffness or swelling causing inability to perform basic self-care functions
Bone Mineral Loss Pediatric < 21 Years	BMD t-score or z-score –2.5 to –1.0 BMD z-score –2.5 to –1.0	BMD t-score or z-score < –2.5 BMD z-score < –2.5	Pathological fracture (including loss of vertebral height) Pathological fracture (including loss of vertebral height)	Pathologic fracture causing life-threatening consequences Pathologic fracture causing life-threatening consequences
Myalgia (non-injection site)	Muscle pain causing no or minimal interference with usual social & functional activities	Muscle pain causing greater than minimal interference with usual social & functional activities	Muscle pain causing inability to perform usual social & functional activities	Disabling muscle pain causing inability to perform basic self-care functions
Osteonecrosis	NA	Asymptomatic with radiographic findings AND No operative intervention indicated	Symptomatic bone pain with radiographic findings OR Operative intervention indicated	Disabling bone pain with radiographic findings causing inability to perform basic self-care functions

SYSTEMIC				
	Grade 1	Grade 2	Grade 3	Grade 4
Acute Systemic Allergic Reaction	Localized urticaria (wheals) with no medical intervention indicated	Localized urticaria with medical intervention indicated OR Mild angioedema with no medical intervention indicated	Generalized urticaria OR Angioedema with medical intervention indicated OR Symptomatic mild bronchospasm	Acute anaphylaxis OR Life-threatening bronchospasm OR laryngeal edema
Chills	Symptoms causing no or minimal interference with usual social & functional activities	Symptoms causing greater than minimal interference with usual social & functional activities	Symptoms causing inability to perform usual social & functional activities	NA
Fatigue Malaise	Symptoms causing no or minimal interference with usual social & functional activities	Symptoms causing greater than minimal interference with usual social & functional activities	Symptoms causing inability to perform usual social & functional activities	Incapacitating fatigue/malaise symptoms causing inability to perform basic self-care functions
Fever (nonaxillary)	37.7°C to 38.6°C 99.8°F to 101.5°F	38.7°C to 39.3°C 101.6°F to 102.8°F	39.4°C to 40.5°C 102.9°F to 104.9°F	> 40.5°C > 104.9°F
Pain- Indicate Body Site See also Injection Site Pain, Headache, Arthralgia, and Myalgia	Pain causing no or minimal interference with usual social & functional activities	Pain causing greater than minimal interference with usual social & functional activities	Pain causing inability to perform usual social & functional activities	Disabling pain causing inability to perform basic self-care functions OR Hospitalization (other than ER visit) indicated
Unintentional Weight Loss	NA	5% to 9% loss in body weight from baseline	10% to 19% loss in body weight from baseline	≥ 20% loss in body weight from baseline OR Aggressive intervention indicated [eg, tube feeding or total parenteral nutrition]

INJECTION SITE REACTION				
	Grade 1	Grade 2	Grade 3	Grade 4
Injection Site Pain (pain without touching) Or Tenderness (pain when area is touched)	Pain/tenderness causing no or minimal limitation of use of limb	Pain/tenderness limiting use of limb OR Pain/tenderness causing greater than minimal interference with usual social & functional activities	Pain/tenderness causing inability to perform usual social & functional activities	Pain/tenderness causing inability to perform basic self-care function OR Hospitalization (other than ER visit) indicated for management of pain/tenderness
Injection Site Reaction (Localized), > 15 Years Pediatric ≤ 15 Years	Erythema OR Induration of 5 × 5 cm to 9 × 9 cm (or 25–81 × cm ²) Erythema OR Induration OR Edema present but ≤ 2.5 cm diameter	Erythema OR Induration OR Edema > 9 cm any diameter (or > 81 cm ²) Erythema OR Induration OR Edema > 2.5 cm diameter but < 50% surface area of the extremity segment (eg, upper arm/thigh)	Ulceration OR Secondary infection OR Phlebitis OR Sterile abscess OR Drainage Erythema OR Induration OR Edema involving ≥ 50% surface area of the extremity segment (eg, upper arm/thigh) OR Ulceration OR Secondary infection OR Phlebitis OR Sterile abscess OR Drainage	Necrosis (involving dermis and deeper tissue) Necrosis (involving dermis and deeper tissue)
Pruritis Associated with Injection See also Skin: Pruritis (itching—no skin lesions)	Itching localized to injection site AND Relieved spontaneously or with < 48 h treatment	Itching beyond the injection site but not generalized OR Itching localized to injection site requiring ≥ 48 h treatment	Generalized itching causing inability to perform usual social & functional activities	NA

ENDOCRINE/METABOLIC				
	Grade 1	Grade 2	Grade 3	Grade 4
Lipodystrophy (eg, back of neck, breasts, abdomen)	Detectable by study participant or caregiver (for young children and disabled adults)	Detectable on physical exam by health care provider	Disfiguring OR Obvious changes on casual visual inspection	NA
Diabetes Mellitus	NA	New onset without need to initiate medication OR Modification of current meds to regain glucose control	New onset with initiation of indicated med OR Diabetes uncontrolled despite treatment modification	Life-threatening consequences (eg, ketoacidosis, hyperosmolar non-ketotic coma)
Gynecomastia	Detectable by study participant or caregiver (for young children and disabled adults)	Detectable on physical exam by health care provider	Disfiguring OR Obvious on casual visual inspection	NA
Hyperthyroidism	Asymptomatic	Symptomatic causing greater than minimal interference with usual social & functional activities OR Thyroid suppression therapy indicated	Symptoms causing inability to perform usual social & functional activities OR Uncontrolled despite treatment modification	Life-threatening consequences (eg, thyroid storm)
Hypothyroidism	Asymptomatic	Symptomatic causing greater than minimal interference with usual social & functional activities OR Thyroid replacement therapy indicated	Symptoms causing inability to perform usual social & functional activities OR Uncontrolled despite treatment modification	Life-threatening consequences (eg, myxedema coma)
Lipoatrophy (eg, fat loss from the face, extremities, buttocks)	Detectable by study participant or caregiver (for young children and disabled adults)	Detectable on physical exam by health care provider	Disfiguring OR Obvious on casual visual inspection	NA

GENITOURINARY				
	Grade 1	Grade 2	Grade 3	Grade 4
Intermenstrual Bleeding (IMB)	Spotting observed by participant OR Minimal blood observed during clinical or colposcopic exam	Intermenstrual bleeding not greater in duration or amount than usual menstrual cycle	Intermenstrual bleeding greater in duration or amount than usual menstrual cycle	Hemorrhage with life-threatening hypotension OR Operative intervention indicated
Urinary Tract obstruction (eg, stone)	NA	Signs or symptoms of urinary tract obstruction without hydronephrosis or renal dysfunction	Signs or symptoms of urinary tract obstruction with hydronephrosis or renal dysfunction	Obstruction causing life-threatening consequences

INFECTION				
	Grade 1	Grade 2	Grade 3	Grade 4
Infection (any other than HIV infection)	Localized, no systemic antiꝑubial treatment indicated AND Symptoms causing no or minimal interference with usual social & functional activities	Systemic antiꝑubial treatment indicated OR Symptoms causing greater than minimal interference with usual social & functional activities	Systemic antiꝑubial treatment indicated AND Symptoms causing inability to perform usual social & functional activities OR Operative intervention (other than simple incision and drainage) indicated	Life-threatening consequences (eg, septic shock)

Basic Self-care Functions: Activities such as bathing, dressing, toileting, transfer/movement, continence, and feeding.

Usual Social & Functional Activities: Adaptive tasks and desirable activities, such as going to work, shopping, cooking, use of transportation, pursuing a hobby, etc.

Appendix 5. Pregnancy Precautions, Definition for Female of Childbearing Potential, and Contraceptive Requirements

1) Pregnancy and Contraception Requirements for Males and Females of Childbearing Potential

The risks of treatment with GS-9620 during pregnancy have not been evaluated in humans. Please refer to the latest version of the investigator's brochure for GS-9620 for the treatment of chronic hepatitis B virus and HIV-1 infection for additional information.

2) Definition of Female of Childbearing Potential

For the purposes of this study, a female subject of childbearing potential is a nonmenopausal female who has not had a hysterectomy, bilateral oophorectomy, or medically documented ovarian failure. This definition includes a pubertal female who has not yet started menstruating. A woman who has had a tubal sterilization is considered to be of childbearing potential.

A female subject may be considered menopausal in either of the following conditions:

- Surgical menopause: Appropriate medical documentation of prior complete bilateral oophorectomy (ie, surgical removal of the ovaries and occurring at the age at which the procedure was performed)
- Spontaneous menopause: Permanent cessation of previously occurring menses as a result of ovarian failure with documentation of hormonal deficiency by a certified health care provider. The worldwide mean age of spontaneous menopause is 49.24 (SD 1.73) years
- A hormonal deficiency should be properly documented in the case of suspected spontaneous menopause as follows:
 - If age ≥ 54 years and with the absence of normal menses: serum follicle stimulating hormone (FSH) level elevated to within the postmenopausal range based on the laboratory reference range where the hormonal assay is performed
 - If age < 54 years and with the absence of normal menses: negative serum or urine human chorionic gonadotropin (hCG) with concurrently elevated serum FSH level in the postmenopausal range, depressed estradiol (E2) level in the postmenopausal range, and absent serum progesterone level, based on the laboratory reference ranges where the hormonal assays are performed

3) Contraceptive Requirements

Male subjects and female subjects of childbearing potential who engage in heterosexual intercourse must agree to utilize protocol specified methods of contraception from the screening/enrollment visit throughout the study period and for 36 days following the last dose of study drug. Female study subjects who are not heterosexually active must provide periodic confirmation of continued abstinence from heterosexual intercourse and regular pregnancy testing while taking GS-9620 or placebo. The investigator will counsel subjects on the protocol specified method(s) for avoiding pregnancy in case the subject chooses to engage in heterosexual intercourse.

Protocol specified contraceptive methods are as follows: (1) a combination of one hormonal method and one barrier method; or (2) use of an intrauterine device (IUD) or tubal sterilization; see [Appendix Table 1](#). Acceptable hormonal methods include injectable progesterone, progesterone implants, combination oral contraceptives, transdermal contraceptive patch, and vaginal ring. An acceptable barrier method is the male condom. Female subjects must use a hormonal method if the partner has a vasectomy. If a subject has undergone tubal sterilization or has had a Copper T 380A IUD or LNG 20 IUD inserted, no other contraception is needed.

If tubal sterilization is via the Essure procedure, verification of tubal blockage by hysterosalpingogram (HSP) must be performed approximately 3 months after microinsertion. Prior to verification, Essure is not considered a reliable form of contraception and the contraception methods described below must be used. Female subjects who utilize hormonal contraceptives as one of their birth control methods must have used the same method for at least 3 months before study dosing.

Female subjects of childbearing potential must have a negative serum pregnancy test at screening and a negative urine pregnancy test at baseline (Day 1) prior to receiving the first dose of study drug. Lactating females must discontinue nursing before IMP administration.

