- 15) Estimated GFR ≥ 60 mL/min according to the Cockcroft-Gault formula for creatinine clearance {[Cockcroft 1976](#)}:
 - i. Male:
$$\frac{(140 - \text{age in years}) \times (\text{wt in kg})}{72 \times (\text{serum creatinine in mg/dL})} = \text{CLcr (mL/min)}$$
 - ii. Female:
$$\frac{(140 - \text{age in years}) \times (\text{wt in kg}) \times 0.85}{72 \times (\text{serum creatinine in mg/dL})} = \text{CLcr (mL/min)}$$
- 16) All subjects must agree to utilize male or female condoms during sexual activity, or practice sexual abstinence for the duration of the study.
- 17) Females of childbearing potential must agree to utilize highly effective contraception methods (as described in [Appendix 5](#)) or be non-heterosexually active or practice sexual abstinence from screening through the duration of study treatment and for 36 days following the last dose of study drug.
 - a) Female subjects who utilize hormonal contraceptive as one of their birth control methods must have used the same method for at least three months prior to study dosing
 - b) Female subjects who have stopped menstruating for ≥ 12 months but do not have documentation of ovarian hormonal failure must have a serum follicle stimulating hormone (FSH) level at screening within the post-menopausal range based on the Central Laboratory reference
- 18) Male subjects must agree to utilize a highly effective method of contraception during heterosexual intercourse (as described in [Appendix 5](#)) or be non-heterosexually active, or practice sexual abstinence from screening throughout the study period and for 90 days following discontinuation of investigational medicinal product

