Appendix Table 1. Protocol Specified Contraceptive Methods

Single Methods	Combination Methods

Intrauterine Devices (IUDs)
 
 • Copper T 380A IUD • LNG 20 IUD 
Tubal Sterilization
	
Estrogen and Progesterone plus Barrier
 
 • Combined oral contraceptives plus condom* • Transdermal patch plus condom* • Vaginal ring plus condom* • Implant plus condom* • Injection plus condom* 
Partner’s vasectomy must be used with a hormonal method.

* (without spermicide and excluding lambskin)

The investigator will counsel all subjects on the most effective method(s) for avoiding pregnancy during the study.

4) Additional Requirements for Male Subjects and Recommendations for Partners of Female Subjects

Male subjects must agree to use condoms (without spermicide and excluding lambskin) during heterosexual intercourse and avoid sperm donation while enrolled in the study and for at least 90 days after administration of the last dose of study drug. Partners of female subjects should be encouraged to use condoms during heterosexual intercourse while enrolled in the study.

Use of condoms, with or without spermicide, has been proven to decrease the risk of transmission of HIV and other sexually transmitted diseases. The use of spermicide is not recommended if the subject or subject’s partner is infected with HIV.

5) Procedures to be Followed in the Event of Pregnancy

Subjects will be instructed to notify the investigator if they become pregnant at any time during the study, or if they become pregnant within 30 days or 4 weeks of last study drug dose. Subjects who become pregnant or who suspect that they are pregnant during the study must report the information to the investigator and discontinue study drug immediately. Subjects whose partner has become pregnant or suspects she is pregnant during the study must report the information to the investigator. Instructions for reporting pregnancy, partner pregnancy, and pregnancy outcome are outlined in Section [7.7.2.1](#).

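### Appendix 5 part 3 ends male contraception 36 days after the last dose, where inclusion criterion 18 requires 90 days

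*Protocol*

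**What the plan says.** Four places in the protocol set post-dose contraception periods.

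- **Appendix 5, part 3 (Contraceptive Requirements).** One sentence covers both sexes: "Male subjects and female subjects of childbearing potential who engage in heterosexual intercourse must agree to utilize protocol specified methods of contraception". The duty lasts "throughout the study period and for 36 days following the last dose of study drug". The methods are "1) a combination of one hormonal method and one barrier method; or (2) use of an intrauterine device (IUD) or tubal sterilization". The same paragraph as the 36 days holds the counselling duty: "The investigator will counsel subjects on the protocol specified method(s) for avoiding pregnancy in case the subject chooses to engage in heterosexual intercourse".
- **Section 4.2, criterion 18 (men).** "Male subjects must agree to utilize a highly effective method of contraception during heterosexual intercourse", with the methods taken from Appendix 5. The period is "throughout the study period and for 90 days following discontinuation of investigational medicinal product".
- **Section 4.2, criterion 17 (females of childbearing potential).** The period is "from screening through the duration of study treatment and for 36 days following the last dose of study drug".
- **Appendix 5, part 4 (additional requirements for men).** "Male subjects must agree to use condoms (without spermicide and excluding lambskin) during heterosexual intercourse and avoid sperm donation while enrolled in the study". Both duties then continue post-dose, with a minimum of 90 days.

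**The concern.** Criterion 18 is what each man agrees to at entry. Appendix 5 is where it sends the reader for the methods. The two give different end dates for the same duty, and the shorter date is the one the protocol sets for women.

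The conflict could reach subjects because the instruction to counsel them stands beside the 36-day figure. A site that reads all of Appendix 5 keeps men on condoms to day 90 but may release the partner's method after day 36. A site that uses part 3 alone would give the wrong end date for the whole duty.

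Appendix 5 part 1 says the risks of the drug in pregnancy have not been evaluated in humans, and Section 7.7.2.1 requires pregnancies in partners of male subjects to be reported. The protocol therefore treats exposure through men as something to guard against, and it chose 90 days to do so.

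**Working it through.** This is a comparison of texts, followed by date arithmetic.

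**1. Periods side by side**

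| Place | Who | Duty | Days after last dose |
|---|---|---|---|
| Criterion 17 | Females of childbearing potential | Highly effective contraception | 36 |
| Criterion 18 | Men | Highly effective contraception, methods from Appendix 5 | 90 |
| Appendix 5 part 3 | Both | Protocol-specified methods | 36 |
| Appendix 5 part 4 | Men | Condoms, no sperm donation | at least 90 |

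Both male-specific texts say 90 and the female-specific criterion says 36. Part 3 is the outlier for men.

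**2. What part 4 leaves open.** In part 3 and Appendix Table 1 the condom appears only in combination with a hormonal method. Part 4 carries the condom and the ban on sperm donation to 90 days. It does not carry the hormonal method, IUD or tubal sterilization beyond the 36 days of part 3.

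**3. Length of the gap.** Take discontinuation of study drug in criterion 18 to mean the last dose. The gap is days 37 to 90: 90 − 36 = 54 days.

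**4. In study days, if dosing is on schedule**

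- Cohorts 1 to 3, last dose Day 71: 71 + 36 = Day 107 and 71 + 90 = Day 161, so the gap is Days 108 to 161 (54 days).
- Cohorts 4 to 6, last dose Day 127: 127 + 36 = Day 163 and 127 + 90 = Day 217, so the gap is Days 164 to 217 (54 days).

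**5. Position of the End of Study visit.** It is due on Day 101 or Day 157, each ± 3 days. 101 − 71 = 30 and 157 − 127 = 30, so it falls 27 to 33 days after the last dose. 36 − 33 = 3 and 36 − 27 = 9, so the visit comes 3 to 9 days before the 36 days run out. It is a scheduled chance to state the correct period.

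**The case against.** The best reply is that criterion 18 may point men to part 4, the only section of Appendix 5 written specifically for them. Apart from the male condom, the part 3 methods are used by the woman, and Appendix 5 never uses the term highly effective. On that reading men owe condoms for 90 days, nothing is missing between days 37 and 90, and part 3 is merely loosely worded.

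This is the weaker reading. Part 3 names male subjects and puts them under the protocol-specified methods. Appendix Table 1 lists the condom only as part of a combination. Criterion 16 already asks every subject to use condoms or abstain for the duration of the study, so criterion 18 is best read as asking for more. Even if the reply were accepted, part 3 would still state a period for men that contradicts criterion 18.

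A second reply is that the 90 days in criterion 18 attach only to abstinence. Criterion 17 is built the same way, and there the period plainly covers every option.

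Three points on reach do stand:

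- Understating the whole period requires a site to overlook both part 4 and criterion 18, which is unlikely. A man who follows criterion 18 breaches nothing.
- Protocol Section 1.4 reports that dosing at 1 to 6 mg had been given and that the 8 mg cohort was under way at the 30 April 2018 data cut. SAP Section 2.1.1 describes the safety committee reviews, including Cohort 6, as already done. A notice can help only men still within 90 days of their last dose, or men enrolled later, for example in the optional cohorts. The documents also do not show that this wording applied when the early cohorts were dosed.
- The consent wording is not available for review, so whether any man was actually told 36 days is unknown.

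**Conclusion.** The concern holds. By the protocol's own terms, Appendix 5 part 3 states the wrong post-dose period for men: 36 days where criterion 18 requires 90.

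For a site that reads the whole appendix, the shortfall is the partner component of the method for 54 days; condom use and the ban on sperm donation are covered. For a site that counsels from part 3 alone, it is 54 of the 90 days for the entire duty.

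This rests on counting criterion 18 from the last dose and on reading its methods as those of part 3 and Appendix Table 1. The documents give no data on exposure through a male subject, so the case rests on the protocol's own 90-day rule and not on shown harm. The number of men affected cannot be determined. No analysis or result depends on it. It should be corrected because it is an operative safety instruction.

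**What to change.** In Appendix 5 part 3, restrict the 36 days to females of childbearing potential, in line with criterion 17. State 90 days after the last dose for male subjects, in line with criterion 18 and part 4. Notify sites so that men are told 90 days no later than the End of Study visit.

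The cost is one amended sentence and a site notice. The SAP needs no change.
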